## **Exploratory Endpoint:**

To explore biomarkers significantly and potentially associated with clinical efficacy

# 10. Safety Evaluation

Timely, accurate, and complete reporting and analysis of safety information from clinical studies are essential to protect patients and investigators and are mandatory by regulatory authorities worldwide. Each AE verbatim term will be coded to a system organ class and preferred term using the Medical Dictionary for Regulatory Activities (MedDRA).

## 10.1 Definition and Classification of Adverse Events

#### **Adverse Events:**

An AE is any untoward medical occurrence in a patient to whom a medicinal product is administered, and which does not necessarily have a causal relationship with this treatment. An AE can therefore be any unfavorable and unintended sign (eg, an abnormal laboratory finding), symptom, or disease temporally associated with the use of a medicinal product, whether considered related to this medicinal product. (As defined by the International Council for Harmonisation of Technical Requirements for Pharmaceuticals for Human Use [ICH]).

It includes any new event, any event worsened from baseline in severity or frequency, or abnormal results of diagnostic procedures, including laboratory test abnormalities.

#### **Serious Adverse Events:**

An SAE, as defined by ICH, as an AE that fulfils one or more of the following criteria at any dose:

- Results in death
- Is life-threatening ((life-threatening refers to a reaction in which the patient was at risk of death at the time of the reaction; it does not refer to a reaction that hypothetically might have caused death if more severe).)
- Requires hospitalization or prolongation of existing hospitalization
- Results in persistent disability/incapacity (The term disability means a substantial disruption of a person's ability to conduct normal life functions.)
- Is a congenital anomaly/birth defect
- Is an important medical event

Note: Medical or scientific judgment should be exercised in deciding whether SAE reporting is appropriate in other situations such as important medical events that may not be immediately life-threatening or result in death or hospitalization but may jeopardize the patient or may require medical or surgical intervention to prevent one of the other outcomes listed in the above definition. These events should usually be considered serious.

Events that are not considered SAEs include planned hospitalization before enrollment

into the clinical study; a disease for elective treatment and unrelated to the indication under study or its treatment; events occurring in an emergency outpatient department and not leading to hospitalization (unless other criteria above are met); part of normal treatment or monitoring of the study indication and unrelated to condition worsening.

If an AE is considered serious, the AE page in the CRF and the SAE Report Form must be completed. The investigator will provide information on severity, start and end dates, relationship to the study drug, actions taken with the study drug, and outcomes.

## **Suspected Unexpected Serious Adverse Reaction:**

For unexpected AEs, their nature or severity is inconsistent with the that of the study drug. For the study drug, the expectedness of an AE will depend on whether it is listed in the Investigator's Brochure of the study drug. For a drug with marketing authorization, the expectedness of an AE will depend on whether it is listed in the summary of product characteristics (SmPC).

### **Severity Assessment:**

For AEs and SAEs, the investigator must assess the severity of the events. According to the NCI CTCAE Version 4.03, the severity of AEs will be graded from 1 to 5. A copy of the NCI CTCAE Version 5.0 can be downloaded from the homepage of the Cancer Therapy Evaluation Program (CTEP) (https://ctep.cancer.gov/protocolDevelopment/electronic\_applications/docs/CTCAE\_v 5\_Quick\_Reference\_5x7.pdf). In those cases where NCI CTCAE is not applicable, the severity should be defined according to the following criteria:

### Grade Definition:

Grade 1 (mild AE): asymptomatic or mild symptoms; usually transient, not requiring treatment, and generally not interfering with daily activities

Grade 2 (moderate AE): Moderate discomfort, interfering with daily activities; usually relieved by basic treatment

Grade 3 (severe AE): Severe incapacitation, inability to perform daily activities, or significantly affecting clinical status, requiring intervention. Hospitalization may or may not be required.

Grade 4 (life-threatening or disabling AE): Life-threatening consequences, life-threatening; requiring hospitalization and clinical intervention.

Grade 5 (AE-related death): Death related to AE

## **Causality Assessment:**

The investigator must determine that the relationship between the administration of the study drug and AEs/SAEs as defined below:

• Unrelated. AEs are not related to the use of the study drug.

- Unlikely/suspicious. AEs that are more likely to have alternative explanations, such as concomitant medications, concomitant diseases, or temporal relationships suggest little causality.
- Possibly. Treatment with the study drug caused or contributed to the AE. Alternative explanations, such as concomitant medications and diseases, are uncertain. The event follows a reasonable temporal sequence from the time of drug administration; therefore, causality cannot be ruled out.
- Probably. AEs are probably caused by the use of the study drug. A reasonable temporal sequence of the event with drug administration exists Alternative explanations don't make sense, such as concomitant medications and concomitant diseases.
- Definitely. AEs that are listed as possible AE reactions and cannot be reasonably explained by alternative explanations, such as concomitant medications and concomitant diseases. The relationship in time is very suggestive (eg, it is challenged and re-challenged).
- Non-evaluable: The evidence for making a clinical judgment of causality is insufficient or incomplete.

# **Treatment-related Mortality:**

If an AE related to the study drug is considered to result in the death, that event will be listed as "treatment-related mortality".

# **10.2** Safety Evaluation

If a patient completes at least 1 month of effective treatment, the patient will be analyzed for safety. The tolerability of treatment will be assessed by evaluating laboratory parameters and AEs. The incidence of all AEs during the treatment and up to 30 days after the last drug administration will be recorded.

AEs will be classified by severity, duration, and frequency. Details of AEs will be listed by patients, including time of onset, duration, toxicity grade, corrective treatment, outcome, and relationship to the investigational product. Safety parameters will be assessed by 2 independent investigators who will assess severity and treatment each time.

Study drug should be discontinued for any uncontrolled non-hematological toxicity that may be associated with the study drug and of Grade 3 or higher, and for any hematological toxicity that meets the criteria. For patients requiring full-dose anticoagulation (eg, heparin), the study drug should be interrupted until the anticoagulation is stable. For patients requiring an invasive procedure or surgery, the study drug must be interrupted. Any other clinically important events, in which the investigator may deem appropriate dose delays, must be discussed with the CRA. Details of drug adjustment and discontinuation criteria, refer to Section 7.4.

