## 8.5.2 Safety Follow-up

Safety follow-up will be performed for all patients who complete or discontinue treatment until 1 year after the last dose of the study drug, or until initiation of a new antineoplastic therapy (whichever occurs first).

Patients will be contacted by phone 1 year after the last dose, or asked to the study site for a safety visit to collect the ongoing AEs or changes in laboratory abnormalities, and to assess new AEs, SAEs, new concomitant medications, or changes in current medications since the last assessment. Any new conditions that occur during the safety follow-up need to be documented in the CRF as appropriate. After the safety follow-up (ie, 28 days after the last dose), there is no need to actively collect AEs. However, if an SAE occurs and the investigator assesses a reasonable causality to the study drug, the SAE should be reported.

AEs (regardless of causality) that do not completely resolve at the end of safety followup must be followed up until recovery (chronic, baseline value, or completely recovery), or clinical stability is achieved.

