# 9. Efficacy Evaluation

## 9.1 Definition

### 9.1.1 General Definition

Evaluable toxicity: All patients who have received at least 1 month of TPM treatment are evaluable for toxicity evaluation from the first treatment.

Evaluable objective response: Only patients who have a measurable disease at baseline, have received at least 1 treatment cycle, and have been re-evaluated for the disease will be considered as evaluable responses. These patients will be categorized for their responses according to the following definitions (Note: Patients who demonstrate objective PD or death by the end of Cycle 1 will also be considered evaluable).

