# 10.4 Reporting of Adverse Events

All AEs and SAEs that occur between the first study-related procedures and within 30 days after the last dose of the study drug will be reported. All AEs, regardless of severity or presumed relationship to the study drug, must be recorded on the CRF using medical terms.

Refer to

(https://ctep.cancer.gov/protocolDevelopment/electronic\_applications/docs/CTCAE\_v 5\_Quick\_Reference\_5x7.pdf) for details. The investigators also need to record their opinions on the relationship between AEs and the study drug on the CRF. All actions required for AE management must be recorded in the source documents. All SAE reports must be submitted within 24 hours. For initial SAEs, all case details should be collected within 24 hours. The initial report must be as complete as possible, including details of the current diseases and SAEs, as well as an assessment of the causality between the event and the study drug. Information that is not available at the time of initial reporting (eg, end date or laboratory values of AEs) must be recorded on subsequent SAE forms when available and/or immediately upon request. The investigator must keep a copy of all SAE information on file. All SAEs that are unresolved at the time a patient discontinues study must be followed until the event is fully resolved, stabilized/sequelae resolved, or baseline (if any) is returned.

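### The safety analysis is limited to patients with at least 1 month of treatment, so toxicity that stops treatment earlier drops out of the AE rates; the AE collection window also has conflicting lengths

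*Supplement*

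**What the plan says.** All references are to protocol version 2.0.

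**Who is analysed.** Section 10.2: "If a patient completes at least 1 month of effective treatment, the patient will be analyzed for safety". Section 9.1.1: "All patients who have received at least 1 month of TPM treatment are evaluable for toxicity evaluation from the first treatment". Section 10.2 asks for treatment that is effective, a word the protocol does not define. Section 11.2 promises counts and incidences of toxicity but names no denominator, and no section defines a safety set based on having taken a dose.

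**When AEs are collected.**
- Section 10.2: "The incidence of all AEs during the treatment and up to 30 days after the last drug administration will be recorded".
- Section 10.4 reports "All AEs and SAEs that occur between the first study-related procedures and within 30 days after the last dose of the study drug".
- Section 8.5.2: "Safety follow-up will be performed for all patients who complete or discontinue treatment until 1 year after the last dose of the study drug". The start of another antineoplastic therapy ends this period sooner. New AEs are assessed at the 1-year contact.
- Section 8.5.2, in its next paragraph: "After the safety follow-up (ie, 28 days after the last dose), there is no need to actively collect AEs".
- Section 7.4 has AEs assessed from the first dose up to the final study visit.

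**The concern.** Completing 1 month is itself an outcome of treatment. Section 10.2 requires study drug to be stopped for uncontrolled Grade 3 or higher related non-hematological toxicity. If that happens in weeks 1 to 4, the same section removes the patient from the safety analysis. The patients lost are those who tolerated the regimen worst.

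The protocol itself expects early reactions. Section 6.2 starts thalidomide at the lower dose in order to watch for rash and numbness. Section 7.1 warns of thromboembolism and Section 7.2 of Grade 3 or 4 cytopenia. In the Waldenström study described in Section 2.3, 3 patients stopped thalidomide within 30 days.

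Safety and tolerance is the first secondary objective, and the trial has one arm, so no comparator would reveal an understated rate.

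The window matters for a different reason. If sites apply different sentences, their AE counts are not comparable. Section 7.1 says neuropathy symptoms may appear after thalidomide is stopped, so whether such a case counts can depend on the sentence applied.

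**Working it through.** The plan states no figure here to reproduce. The check compares the definitions and then sizes the effect under stated assumptions.

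**1. Does any text override the 1-month rule?** Sections 9.1.1 and 10.2 agree with each other. Section 11.2 gives no denominator. Section 11.1 describes excluded and dropout patients one by one, but that is a listing and does not enter an incidence.

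For patients who reach 1 month, Section 9.1.1 counts toxicity from the first treatment. Early events are therefore lost only for patients who do not reach it.

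Section 9.1.1 also keeps patients who die or progress by the end of Cycle 1 evaluable for response, with no matching exception for toxicity. A toxic death in week 3 counts for response and not for safety.

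**2. Effect on a reported rate.** Inputs:
- N = 42, the planned enrolment in Section 4.5, assumed all treated.
- k = patients stopped before 1 month by the toxicity being counted (assumed).
- y = cases of that toxicity among the other 42 − k patients (assumed).

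Rate under the plan: y/(42 − k). Rate in all treated patients: (y + k)/42.

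Difference: (y + k)/42 − y/(42 − k) = k(42 − k − y) / [42(42 − k)].

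This is positive unless every remaining patient has the event, so the plan's rate is too low. For k = 4, y = 4 the difference is 4 × 34/(42 × 38) = 136/1596 = 8.5 percentage points.

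Rates with exact (Clopper-Pearson) 95% limits:

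| k | y | Under the plan | All treated |
|---|---|---|---|
| 1 | 0 | 0/41 = 0% (0 to 8.6) | 1/42 = 2.4% (0.1 to 12.6) |
| 1 | 4 | 4/41 = 9.8% (2.7 to 23.1) | 5/42 = 11.9% (4.0 to 25.6) |
| 3 | 4 | 4/39 = 10.3% (2.9 to 24.2) | 7/42 = 16.7% (7.0 to 31.4) |
| 4 | 0 | 0/38 = 0% (0 to 9.3) | 4/42 = 9.5% (2.7 to 22.6) |
| 4 | 4 | 4/38 = 10.5% (2.9 to 24.8) | 8/42 = 19.0% (8.6 to 34.1) |
| 6 | 0 | 0/36 = 0% (0 to 9.7) | 6/42 = 14.3% (5.4 to 28.5) |
| 6 | 4 | 4/36 = 11.1% (3.1 to 26.1) | 10/42 = 23.8% (12.1 to 39.5) |

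The k = 6 rows take the Waldenström rate of 3/20 = 15% (0.15 × 42 = 6.3). That study was in another disease and started at 200 mg, so these rows are a high case and not a forecast.

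**3. The AE windows side by side.**

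| Section | Start | End |
|---|---|---|
| 7.4 | First dose | Final study visit (follow-up runs 2 years from end of treatment, Section 8.5.1) |
| 8.5.2, first and second paragraphs | Not stated | 1 year after last dose, or new therapy if earlier |
| 8.5.2, second paragraph, later sentence | Not stated | 28 days after last dose |
| 10.2 | During treatment | 30 days after last dose |
| 10.4 | First study-related procedure | 30 days after last dose |

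That is three lengths after the last dose, a fourth end point in Section 7.4, and two explicit start points. Section 8.5.2 contradicts itself: 365 days against 28 is a factor of about 13.

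The anchor is also loose. Section 4.2 allows up to half a year of prednisone, 1 year of methotrexate and 2 years of thalidomide. The last doses of different study drugs can thus lie up to 24 − 6 = 18 months apart.

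**The case against.** The strongest reply is that early toxicity stays visible. Section 10.4 puts all AEs on the case report form from the first study procedure and requires SAE reports within 24 hours. Section 5.3 records the reason for stopping, Section 11.1 describes dropouts individually, Section 10.1 lists treatment-related deaths with no 1-month condition, and the monitoring committees see the accumulating safety data. All of this stands. It shows that the data will exist and that nothing is hidden from oversight. It does not correct the incidence rates.

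A second reply is that neither sentence says that only these patients are analysed, whereas the response definition in Section 9.1.1 does use that word. The point about wording is fair, but with two matching definitions and no other safety set, the restrictive reading is the one an analyst would follow.

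Third, the number of early stops is assumed, and the protocol's own experience with the regimen is mild: 20 patients, with one Grade 3 nausea and no other Grade 3 or higher reaction (Sections 2.2 and 2.6.2). With one early stop the error is modest, 9.8% against 11.9%. This limits the expected size, but does not remove the bias.

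On the window, 28 against 30 days is trivial, and a 30-day reporting period can coexist with a 1-year contact. Twice-yearly visits after the early-withdrawal assessment also cover long-term toxicity (Section 8.4), and unresolved AEs are followed to recovery or stability (Section 8.5.2). What remains is the contradiction inside Section 8.5.2, the further end point in Section 7.4, and no statement of which window feeds the incidence tables.

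**Conclusion.** The point holds on both parts. As written, the safety analysis conditions on having got through 1 month of treatment, and rates of treatment-stopping early toxicity will be too low whenever such cases occur. For an overall rate with four cases among the remaining patients, the understatement runs from about 2 percentage points with one early stop (9.8% against 11.9%) to about 13 with six (11.1% against 23.8%). With no other cases, four early stops turn 9.5% into zero.

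These sizes rest on assumed values of k and y, on all 42 patients being treated, and on the early stops being caused by the toxicity counted. Patients who stop early without that toxicity would pull the error the other way, because they leave only the denominator.

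The conflict between AE windows is a matter of text and needs no assumption. The primary endpoint, CRR, is not affected. The change should still be made before analysis, because the first-listed secondary objective depends on it.

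**What to change.** 1. In Sections 9.1.1 and 10.2, define the safety set as every patient who received at least one dose of any study drug, and name that set as the denominator in Section 11.2. Delete the 1-month condition and the undefined word effective.
2. Reconcile Sections 7.4, 8.5.2, 10.2 and 10.4 to one AE window with one start and one end, counted from the last dose of the last study drug taken. The sponsor must choose the length; this review does not propose one.
3. Tabulate AEs within that window as the main incidence, and report later events, up to the 1-year contact, separately.

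The cost is wording only. Section 10.4 already has every AE recorded from the first study procedure, so the safety-set change needs no new data. The reported toxicity rates may come out slightly higher.

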## 5.2 Inclusion and Exclusion Criteria

#### 5.2.1 Inclusion Criteria

- 1. Patients who fulfill the diagnostic criteria for T-LGLL or CLPD-NK specified in the 2016 WHO Classification of Lymphoid Neoplasms [1]
- 2. Patients are fully informed about the study and willing to participate in the study and provide written ICF
- 3. Male or female, aged  $\geq$ 18 years
- 4. Treatment-naive patients, or patients treated with or relapsed from a non-methotrexate/ thalidomide-based regimen
- 5. Patients with at least one of the following indications for LGLL treatment:
  - a. ANC  $<0.5 \times 10^9$ /L, or neutropenia with recurrent infections
  - b. Hemoglobin <100 g/L, or requiring infusion of red blood cells
  - c. Platelets level  $< 50 \times 10^9 / L$
  - d. Concomitant autoimmune diseases requiring treatment
  - e. Symptomatic splenomegaly
  - f. Severe B symptoms (fever of unknown cause with body temperature over 38 °C; night sweats; weight loss of ≥10% within half a year)
  - g. Pulmonary hypertension
- 6. Patients with Eastern Cooperative Oncology Group (ECOG) score of 0 to 2 (Appendix 1)
- 7. Patients with life expectancy  $\geq 6$  months.

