# 6 Treatments

# **6.1 Treatment Regimen**

Treatment will be provided in 3-month cycles. Patients will receive thalidomide of 50 to 100 mg orally QD before bedtime, methotrexate of 10 mg/m² orally once weekly, and prednisone of 0.5 to 1 mg/kg orally QOD. Prednisone will be tapered after 3 months of dosing and dosed for up to 6 months. Methotrexate will be dosed for up to 1 year. Thalidomide will be dosed for up to 2 years or discontinued at the investigator's discretion based on clinical symptoms. Efficacy was evaluated after 3 months of treatment, if PR or above response to treatment, the initial treatment regimen will be continued. If there is no clinical benefit after 6 months of initial treatment, patients will switch to the second-line treatment was and will be withdrawn from the study.

Dosage and administration for study drugs are shown in the following table:

TPM Regimen	Dosage and Administration
Methotrexate	10 mg/m  orally, once weekly
Prednisone	0.5–1 mg/kg orally, every other day
Thalidomide	50–100 mg orally, once daily before bedtime

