# **6.3** Concomitant Medications and Supportive Care

## **6.3.1** Prophylactic Medications

Patients will be instructed not to take any additional medication (including over-the-counter drugs) during the study without consultation with the investigator. At each visit, the investigator will ask the patient about any new medication he/she is taking or has taken since the start of the study drug.

When combined with thalidomide, aspirin will be taken orally at 100 mg QD for antiplatelet therapy to prevent thrombosis.

For all patients for long-term use of low doses of methotrexate, folate supplementation (1 mg/day) is recommended to use to reduce the risk of some common methotrexate toxicities and the possibility of treatment discontinuation. The dosage of folate can be increased as needed to a maximum of 5 mg/day, depending on the reported residual symptoms. Folinate can be used to replace folate. Daily supplementation with folic acid or weekly supplementation with folinate can also prevent increases in plasma homocysteine concentration, which will be induced by methotrexate treatment without supplementation.

When combined with prednisone, calcium carbonate will be administered orally at 1 g QD and calcitriol will be administered orally at 0.25 µg twice daily to prevent osteoporosis; at the same time, proton pump inhibitor will be administered orally to inhibit gastric acid secretion and prevent gastrointestinal reactions.

Patients with positive hepatitis B surface antigen should receive routine examination of the HBV DNA copy number and be administered with anti-hepatitis B therapy (lamivudine or entecavir). Treatment in the active phase of the hepatitis B virus should be avoided. During treatment and within 6 months after treatment, lamivudine or entecavir should be administrated for prophylaxis, and hepatitis B DNA copy number quantification should be monitored during treatment (once every 1 to 2 months).

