## **6.3.2** Permitted Medications

The investigator may prescribe any concomitant medication or therapy deemed necessary to provide adequate supportive treatment throughout the study, including those listed below:

Standard supportive treatment (antiemetics, antidiarrheals, anticholinergics, spasmodic drugs, antipyretics, antihistamines, analgesics, and other medications designed to treat the symptoms or signs) will be administered as clinically indicated according to local standard of care and when deemed necessary by the investigator.

- Growth factor support, erythropoietin, and blood product transfusion are allowed for the treatment of symptoms or signs of neutropenia, anemia, or thrombocytopenia according to local standard of care.
- Infectious complications with documented evidence should be treated with oral or intravenous antibiotics, or other anti-infective drugs that the investigator considers appropriate for the infectious condition according to local standards

of care. If clinically indicated, the investigator may administer prophylactic anti-infective therapy to patients according to local standards of care.

- Prevention of tumor lysis syndrome (TLS): For patients with elevated risk of TLS such as high tumor load and renal impairment, adequate hydration and alkalinization should be performed during treatment according to clinical practice, and blood chemistry should be closely monitored.
- Prevention and treatment of HBV activation.
- Other medications for concomitant diseases: Treatment for hypertension, diabetes, etc.
- If a patient experiences an AE during study treatment, the investigator should provide appropriate treatment according to clinical practice, including but not limited to antiemetics, hepatoprotective drugs, drugs for increasing leukocyte, transfusion/blood products, anti-infection drugs, and drugs causing QTc prolongation.

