# 6.4 Source and Use of Study Drugs

The study drugs in this study include thalidomide, methotrexate, and prednisone.

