# 7.4 Guidelines for Dose Adjustment and Discontinuation

In the event of toxicity, the investigator should accurately assess the severity of AEs and serious adverse events (SAEs) based on the patient's condition and the National Cancer Institute (NCI) Common Terminology Criteria for Adverse Events (CTCAE, Version 5.0). Appropriate medication (including infusions, cytokine growth factors, antiemetics, antidiarrheals, etc.) should be administered to treatment AEs. All AEs will be assessed from the time of the first dose of the study treatment until the final study visit. Patients who have experienced AEs may be followed up after the EOS visit for additional assessments until the AE resolves or is deemed stable.

For patients who are unable to tolerate the protocol-specified administration regimen, treatment discontinuation or dose adjustments are allowed. Before treatment discontinuation and dose adjustment, the attribution of AEs to the 3 drugs (thalidomide, methotrexate, and prednisone) should be determined. For non-hematological toxicities attributable to methotrexate and prednisone (not thalidomide), administration of thalidomide may be continued.

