## 7.4.3 Dose Adjustment and Discontinuation of Prednisone

The initial dose of prednisone is 0.5 mg/kg QOD, which should be adjusted according to the hematologic index. Actively monitor blood pressure and blood glucose, and observe adverse reactions of glucocorticoids. If there are adverse reactions of Grade 1 or 2, the dose can be reduced. If adverse reactions with ≥ Grade 3 occur, dose can be gradually reduced and eventually discontinued. If steroid-induced acute psychotic symptoms occur and antipsychotics are ineffective; or if corneal ulcers caused by the herpes virus occur, which can quickly lead to corneal perforation and may result in permanent blindness, discontinue the use of prednisone immediately or rapidly reduce the dosage significantly, instead of reducing it gradually.

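### Aspirin is mandatory with thalidomide without exception, so restarting under 10.2 can add it to full-dose anticoagulation; 10.2 also does not name which drug is held

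*Supplement*

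**What the plan says.** All references are to the version 2.0 protocol.

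- **Aspirin (6.3.1).** "When combined with thalidomide, aspirin will be taken orally at 100 mg QD for antiplatelet therapy to prevent thrombosis". No exception follows for anticoagulation or for a low platelet count.
- **Holding treatment (10.2).** For a patient who needs full-dose anticoagulation, "the study drug should be interrupted until the anticoagulation is stable. For patients requiring an invasive procedure or surgery, the study drug must be interrupted". The drug is in the singular and is not named. Section 10.2 then refers to 7.4 for details.
- **What the study drugs are (6.4).** "The study drugs in this study include thalidomide, methotrexate, and prednisone".
- **Entry (5.2.1, criterion 5).** "Patients with at least one of the following indications for LGLL treatment", one of which is platelets below 50 × 10⁹/L.
- **Prednisone (6.1, 6.2, 7.4.3).** "Prednisone will be tapered after 3 months of dosing and dosed for up to 6 months". Section 6.2 withdraws it in 5 mg steps. Section 7.4.3 allows gradual reduction for reactions of Grade 3 or higher. In two named emergencies (steroid psychosis not responding to antipsychotics, and herpetic corneal ulcer) it says to "discontinue the use of prednisone immediately or rapidly reduce the dosage significantly, instead of reducing it gradually".
- **General rules.** Before a dose change, 7.4 says "the attribution of AEs to the 3 drugs (thalidomide, methotrexate, and prednisone) should be determined". For an adverse event on treatment, 6.3.2 says "the investigator should provide appropriate treatment according to clinical practice".

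**The concern.** Section 2.6.2 ranks venous thromboembolism among thalidomide's most severe toxicities, so the plan should be safe to follow literally when one occurs. Two stated rules, each reasonable alone, combine badly. One ends the hold when anticoagulation is stable; the other makes aspirin compulsory whenever thalidomide is taken. A patient who restarts is then prescribed both, and the protocol does not address the added bleeding risk.

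The aspirin rule also reaches patients whose reason for entering is severe thrombocytopenia. That part does not depend on 10.2.

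The smaller issue is that a multicentre protocol with three study drugs should not tell sites to interrupt an unnamed one. A site that takes the wording to mean all three would also stop the steroid at a time of acute illness or surgery.

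**Working it through.** The plan gives no figure to reproduce. The check is mainly a comparison of the rules, followed by a small calculation of how often they might matter.

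**1. Aspirin with anticoagulation**

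| Stage | 10.2 | 6.3.1 |
|---|---|---|
| Full-dose anticoagulation starts | Study drug held | If thalidomide is held, the aspirin tied to it arguably lapses |
| Anticoagulation stable | Hold ends | If thalidomide resumes, aspirin 100 mg daily is required again |
| Afterwards | No further rule | Aspirin continues alongside the anticoagulant |

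The result needs only that thalidomide be among the drugs resumed. It can apply at any point in the thalidomide course, up to 24 months.

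**2. Does another rule suspend aspirin?**

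- 7.4 and 7.4.1 to 7.4.3 contain no rule for thrombosis, anticoagulation or procedures; 7.4.1 adjusts thalidomide for neuropathy.
- 6.3.2 permits treatment by clinical practice but does not switch off a compulsory co-medication.
- 6.3.3 does not list anticoagulants or their use with aspirin.
- The Grade 3 rule in 10.2 concerns uncontrolled toxicity, and withdrawal criterion 3 concerns toxicity that cannot be relieved. A clot under stable anticoagulation need not meet either.

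**3. Aspirin with low platelets**

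Platelets below 50 × 10⁹/L qualify a patient under 5.2.1, and the exclusions in 5.2.2 set no lower platelet limit. Section 6.3.1 then requires aspirin from the start of thalidomide. Section 7 also lists Grade 3 or 4 thrombocytopenia as reported with thalidomide and with methotrexate. The documents do not say how many patients will enter by this route; it is one of seven alternative indications.

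**4. How often anticoagulation might arise**

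Inputs: the site's own pilot of the regimen had 20 patients (2.5) and no Grade 3 or higher reaction except one nausea (2.6.2, assuming that statement refers to those 20). The 25-patient thalidomide–cyclophosphamide study reported no thrombosis (2.5). Planned enrolment is 42 (4.5).

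With zero events, the Clopper–Pearson two-sided 95% upper limit is 1 − 0.025^(1/n).

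- n = 20: 1 − 0.025^(1/20) = 0.168; × 42 = 7.1 patients
- n = 25: 1 − 0.025^(1/25) = 0.137; × 42 = 5.8 patients

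These are ceilings on thrombosis, and in the pilot on Grade 3 or higher thrombosis only. They do not estimate how many patients would be anticoagulated, restart thalidomide and take aspirin, which is a subset. Version 2.0 also excludes high Caprini risk, which should lower the rate by an amount the documents do not give.

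**5. Which drug is held**

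Section 6.4 lists three drugs and 10.2 names none. Attribution under 7.4 applies to adverse events. It would usually point to thalidomide for a thrombosis, because 7.1 lists thromboembolism while 7.2 and 7.3 do not. It cannot select a drug for a planned procedure. Read literally, 10.2 covers prednisone too and offers no taper, while 6.2 and 7.4.3 make gradual reduction the default and 7.3 warns of adrenal unresponsiveness in surgery or disease. This matters for at most 6 of 24 treatment months (6/24 = 25%).

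Expected major surgery is excluded by 5.2.2, so the procedure sentence mainly concerns unplanned surgery and lesser procedures. The bone marrow biopsy listed in 8.2 for the end of Cycle 1 could itself count as one, although the table in 8.3 makes it conditional on need.

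**The case against.** The best case for leaving the text alone is that the harm needs a chain of events: a clot or other reason for full-dose anticoagulation, a decision to resume thalidomide, and a physician already treating the clot who still prescribes prophylactic aspirin. Resumption is not compulsory. Section 6.1 lets the investigator stop thalidomide, and withdrawal criteria 6 and 9 allow it as well. Blood counts are listed throughout Months 1 to 24 and coagulation is checked each cycle. Section 7.5 sends temporary stops for unrelated illness to consultation with the investigator.

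Most of this stands as a limit on frequency. It does not remove the point, because safety would then rest on a clinician departing from a rule written as mandatory. Monitoring platelets also does not tell the site to stop aspirin.

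A reader might go further and infer that 10.2 contradicts 7.4.3 by ordering an abrupt steroid stop. The documents do not support that. Section 7.4.3 is permissive, concerns prednisone's own adverse reactions and does not expressly forbid a short hold. A temporary interruption of unstated length is also not comparable with the weeks-long permanent withdrawal in 6.2; with alternate-day dosing, a pause of a day or two misses about one dose. What remains is an absent safeguard. A reader might also take the upper limits above as the number of patients exposed to aspirin plus anticoagulation; they bound a different and larger group.

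**Conclusion.** The aspirin point holds. Following 6.3.1 and 10.2 as written gives aspirin on top of full-dose anticoagulation if thalidomide resumes, and 6.3.1 alone gives aspirin to patients entering with platelets below 50 × 10⁹/L. The unnamed drug in 10.2 is a secondary clarification.

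The severity is minor to moderate safety wording. Few patients are likely to reach the anticoagulation situation, and the number entering with low platelets is not given. The conclusion assumes that sites follow the text literally and that thalidomide is among the drugs resumed. There is no claimed effect on the complete remission rate, sample size or analysis.

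**What to change.** **6.3.1, after the aspirin sentence:** *Prophylactic aspirin is not given while the patient is on full-dose anticoagulation, or while platelets are below 50 × 10⁹/L.* The cut-off is the protocol's own entry value; the investigators may state another.

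**10.2, replacing the unnamed drug:** *For thromboembolism or full-dose anticoagulation, thalidomide is interrupted. For an invasive procedure or surgery, thalidomide is interrupted and methotrexate is held at the investigator's judgement. In either case prednisone is continued or tapered, not stopped abruptly.* Naming methotrexate for procedures matters because the present wording can cover it, and a sentence naming thalidomide alone would narrow that precaution.

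The cost is a few sentences, with no change to sample size, visits or analyses. The small downside is less antiplatelet prophylaxis in patients with low platelets, which the choice of cut-off should weigh.
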